The study design will include a surgery group and a surgery plus group. All patients will have been scheduled to undergo surgical evacuation of SDH as standard treatment. These patients will be approached by one of the investigators with information about the study. After consent, the patient will be randomly assigned to either the surgery or the surgery plus group. A random number list will be provided to the investigators to use for assignment of patients to the surgery or surgery plus group. Patients randomized in the surgery plus group will subsequently undergo endovascular embolization within 72 hours after surgery and during their hospital stay. Patients in the surgery group will not undergo

the embolization procedure. CT scans will be performed as described above as standard care for this population. Follow-up care during their hospitalization will be the same for both groups barring a complication. All procedures (surgical evacuation and endovascular embolization) performed are standard treatment options for SDH that are used at our institution and facilities across the country

c. Data Types and Source Records:

Data will be collected from medical records and will include the following: name, medical record number, age, sex, GCS at admission, IPH volume, whether the patient had surgery, length of stay in the ICU and hospital, IPH volume post-operatively from CT scans, anticoagulant use, history of brain trauma, and any complications (AEs or SAEs).

The study information will be entered into spreadsheets and stored on the secure drive provided by Information Technology specifically for the study.

d. Describe the procedures performed to lessen the probability or magnitude of risks

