All data will be managed in a secure format and according to all applicable regulatory guidelines. All medical records information will be entered into the secure drive by the PI or designated study team members. There will be a separate key to link the entries on the data collection form using an assigned study ID# and the patient medical records. The key will be stored on the secure drive. Only the approved investigator or study team members with username/password access will review medical records and the study information that is collected and stored on the secure drive. Women of child-bearing potential are routinely assessed for pregnancy during the pre-operative workup; any with a positive pregnancy test will not be considered for the study, either as treatment or control subjects. Endovascular embolization and imaging are approved and widely used standard treatment options for SDH but carries the risks of groin hematoma, infection, and embolic stroke. In the event of groin hematoma, pressure is applied to the site, evidence of infection would be treated with appropriate antibiotics, and the AU acute stroke protocol would be implemented in the event of an embolic stroke. Study investigators are experienced in performing the procedure and caring for the patients.

If the patient's clinical picture indicates that the embolization procedure is necessary, the patient would not participate in the study. If this determination is made following consent, the patient would be considered a screen failure.

e. Describe the duration of an individual subject's participation in the study and the time involved also include the overall duration of the project:

The duration of subject participation may range from 2 weeks to 3 months following surgical intervention. These are typical follow-up timelines for patients undergoing treatment for SDH. Study information collected from medical records will extend from the time of diagnosis until the completion of follow-up visits.

9. Data and Specimen Management

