The plan might include establishing a data monitoring committee and a plan for reporting data monitoring committee findings to the IRB and the sponsor.

a. Describe the plan to periodically evaluate the data collected regarding both harms and benefits to determine whether subjects remain safe.

A Data Safety Monitoring Board will be established to assess harms and benefits to subjects. The DSMB will evaluate safety data every 6 months during the trial and at the reporting of any serious adverse event.

b. Describe what data are reviewed, including safety data, untoward events, and efficacy data.

The data collection form and all AEs and SAEs will be reviewed, including whether repeat surgery is needed, length of ICU stay and hospitalizations, and any complications/adverse events that occur.

c. Describe how the safety information will be collected (e.g., with case report forms, at study visits, by telephone calls with participants).

The information will be collected from medical records and entered into the data collection form and/or AE/SAE form.

d. Describe the frequency of data collection, including when safety data collection starts.
 
Data collection, including safety information, will begin as soon as patients are enrolled and will last up to three months post-procedure.

e. Describe who will review the data.
 
Members of the DSMB will include [name] and [name]. Both are board-certified neurosurgeons who have completed CITI training.

f. Describe the frequency or periodicity of review of cumulative data.
 
Every 6 months and at the report of any SAE.

g. Describe any conditions that trigger an immediate suspension of the research.
 
If the embolization procedure is associated with statistically significant increased risks to the subject

11. Withdrawal of Subjects

N/A

a. If applicable, describe anticipated circumstances under which subjects will be withdrawn from the research without their consent.
 
Physicians may determine that it is not in the best interest of the patient to undergo the embolization procedure; the patient would be removed for their safety. The patient may also be removed from the study if the physicians determine that another type of treatment would be more beneficial.
	 N/A

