
b. If applicable, describe any procedures for orderly termination.
 
The procedure would not be done.
	 N/A

c. If applicable, describe procedures that will be followed when subjects withdraw from the research, including partial withdrawal from procedures with continued data collection.
 
Subjects may choose to discontinue their participation in the study at any time by notifying the PI. To withdraw from the study individuals are asked to send a written letter to the PI. Data collection for the subject will stop, but data already collected will continue to be used. Subjects may, at any time, change their mind and decide not to have the embolization procedure by letting the study doctors know their wishes. If the embolization procedure is not done, the patient will be included in the analysis as they were randomized.
	 N/A

12. Risks to Subjects

a. List the reasonably foreseeable risks.

There is a potential risk in breach of confidentiality. Endovascular embolization is an accepted standard of care treatment for subdural hematoma but carries the additional risk of groin hematoma, infection, and embolic stroke. The risks of the procedure will be addressed with subjects randomized to the procedure. Control subjects will have no further risks associated with participation.

b. If applicable, describe any costs that subjects may be responsible for because of participation in the research.

The patient's insurance will be billed for the endovascular embolization procedure that is standard clinical care. The patient will be responsible for paying for the care they would normally receive for their condition, as well as for all co-pays, deductibles and denied claims. The embolization procedure and the surgery-embolization procedure combination have been standard practice for the last three years and insurance companies typically pay when both procedures are done in a single hospitalization.

N/A

c. If applicable, describe risks to others who are not subjects.

Click here to enter text.

X N/A

13. Potential Benefits to Subjects

Describe the potential benefits that individual subjects may experience from taking part in the research
There is no benefit guaranteed to the subjects. It is hoped that the results of this study will benefit patients in the future.

14. Confidentiality

Describe the procedures for maintenance of confidentiality.

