- *An individual with durable power of attorney for health care*
- *Legal guardian*
Next of kin 18 years of age or older:
 - *Spouse*
 - *Child*
 - *Parent*
 - *Sibling*
 - *Grandparent*
 - *Grandchild*
 - *Close friend*

Based upon the investigator's assessment, the patient may be deemed able to provide meaningful assent, and every effort will be made by the investigators to review the assent document with the subject in a manner and language they can understand, explaining the purpose, procedures, risks and benefits, and assuring that the patients understands. If the patient provides assent, the LAR will also be used to provide consent. During the course of their participation, the subject will be re-assessed by the investigators to determine whether their decision-making capacity has changed and if consent/assent is possible. If a subject regains decision-making capacity and indicates they do not wish to participate, the subject will be withdrawn.

17. Compensation for Research-Related Injury

This section is not required when research involves no more than Minimal Risk to subjects. **N/A**

a. Describe the available compensation in the event of research related injury.

In the event that this research related activity results in an injury, treatment will be made available including first aid, emergency treatment, and follow-up care as needed. Cost for such care will be billed in the ordinary manner to the patient or the patient's insurance company. No reimbursement, compensation, or free medical care is offered by Augusta University.

18. Qualifications to Conduct Research and Resources Available

Describe the qualifications of you and your staff to conduct this research. The IRB is looking for information such as area(s) of expertise, past research experience, relevant certifications, etc.

For international research or research with vulnerable populations, describe the qualifications (e.g., training, experience, oversight) of you and your staff as required to conduct the research. When applicable describe the knowledge of the local study sites, culture, and society. Provide enough information so the IRB knows that you have qualified staff for the proposed research.

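### Withdrawal from the study ends all data collection (section 11c), so later reoperations and complications that remain in the routine chart are lost, with no option for continued record review

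*Combined protocol and SAP*

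**What the plan says.** Section 11c describes two routes. A subject may leave the study by notifying the principal investigator, with a written letter requested; then "Data collection for the subject will stop, but data already collected will continue to be used". Separately, a subject may tell the study doctors that they do not want embolization; for that route the text is "If the embolization procedure is not done, the patient will be included in the analysis as they were randomized". It does not say outright that data collection continues for these patients. The form's question for 11c asks about partial withdrawal with continued data collection, but the answer offers no way to leave the study and still permit record review.

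Section 16 adds a third route, for patients enrolled through a legally authorized representative: "If a subject regains decision-making capacity and indicates they do not wish to participate, the subject will be withdrawn".

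The outcomes come from the chart. Section 8a describes surgery, embolization and CT as standard treatment, with data collection as the research procedure. Section 8c says: "Data will be collected from medical records and will include the following". For safety, section 10c says: "The information will be collected from medical records and entered into the data collection form and/or AE/SAE form", and section 10d says that collection "will last up to three months post-procedure". On duration, section 8e says "The duration of subject participation may range from 2 weeks to 3 months following surgical intervention", and adds: "These are typical follow-up timelines for patients undergoing treatment for SDH".

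Section 9a compares additional decompression between groups by chi-square test. Neither 9a nor any other section states how a patient with incomplete follow-up enters that test, and section 9b states no allowance for dropout.

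**The concern.** Surgery and any embolization are over within the first days, since embolization falls within 72 hours of surgery. The follow-up CT comes at about 4-6 weeks and collection may run to three months. For most of that time, withdrawal spares the subject no study visit or test; it only stops someone reading the chart. What is given up is the outcome on which the trial is powered, together with later complications, which the monitoring board is also meant to see.

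A subject who leaves at week 2 and is reoperated at week 5 has a study record showing no reoperation. With few events expected, a small number of such cases matters. If leaving is related to arm or to recovery, the comparison can also be biased, and no analysis can recover outcomes that were never collected.

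**Working it through.** **Inputs.** From sections 9b and 4: reoperation 35% (control) and 5% (treatment), alpha 0.05, chi-square test, 30 per group. The documents give no withdrawal rate, so 10% and 20% are assumptions used to show a range. Withdrawal is taken to occur before any reoperation, because events already recorded are kept.

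**1. Reproduce the plan's sample size.** With p̄ = (p1 + p2)/2,

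n = [1.960·√(2p̄(1−p̄)) + z_power·√(p1(1−p1) + p2(1−p2))]² / (p1−p2)².

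For 0.35 versus 0.05, p̄ = 0.20. The first term is 1.960·√0.32 = 1.1087, and the second root is √0.275 = 0.5244. At 80% power, n = (1.1087 + 0.8416·0.5244)²/0.09 = 26.7, so 27. All six entries of the table in 9b reproduce (27/31/36 and 43/49/57), two-sided and without continuity correction.

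**2. Power with every outcome known.** z = (0.30·√30 − 1.1087)/0.5244 = 1.019, so power is 84.6%.

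**3. Power with equal loss in both arms.** The plan does not choose between the two treatments of lost patients below, so both are shown.

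- *Excluded, 10% loss:* 27 per group. z = (0.30·√27 − 1.1087)/0.5244 = 0.858, power 80.5%.
- *Kept as event-free, 10% loss:* rates become 0.35·0.9 = 0.315 and 0.05·0.9 = 0.045. z = (0.27·√30 − 1.0649)/0.5087 = 0.814, power 79.2%. The observed difference shrinks from 30 to 27 points.
- *20% loss:* 75.4% if excluded (24 per group), 72.9% if kept as event-free.

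Since 27/0.9 = 30, a sample of 30 per group has room for about 10% loss at 80% power under exclusion.

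**4. Sensitivity to one event.** Expected events are 0.35·30 = 10.5 and 0.05·30 = 1.5. Uncorrected chi-square, 30 per group:

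- 8 versus 2: 60·(8·28 − 2·22)²/(10·50·30·30) = 4.32, p = 0.038.
- 7 versus 2, with one control reoperation unseen and that patient kept as event-free: 60·(7·28 − 2·23)²/(9·51·30·30) = 3.27, p = 0.071.
- The same patient excluded, 7/29 versus 2/30: 59·(7·28 − 2·22)²/(9·50·29·30) = 3.48, p = 0.062.

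**5. If only one arm loses patients.** Take no true effect, 35% in both arms, with loss only in the embolization arm and lost patients kept as event-free. A 10% loss produces a false benefit of 0.35·0.10 = 3.5 points, and exact two-sided type I error rises from 4.8% to 5.7%. A 20% loss gives 7 points and 8.7%. These show what such an imbalance would do; they do not forecast one.

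**The case against.** The strongest reply is that record review is the research activity in this trial, so withdrawing from the research naturally ends record review. That is a legitimate reading, and a subject's refusal of access must be honoured. It does not explain why a subject who would allow the chart to be read is given no means of saying so.

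Several stronger readings are tempting, and the documents do not support them.

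- **That withdrawn patients will be counted as event-free or dropped.** No section says either. The plan is silent, and reoperations before withdrawal are kept.
- **That all patients who refuse embolization are lost.** Section 11c keeps them in the analysis as randomized; only continued collection is left unstated.
- **That the extra procedure and its bill will drive withdrawal in one arm.** A patient wishing to avoid either can simply decline embolization, and after embolization withdrawal avoids neither. This mechanism is weak.
- **That stopping early contradicts section 10d.** Three months is stated there as an upper limit, and 8e allows participation as short as 2 weeks.
- **That section 16 causes imbalance.** It says only that the subject is withdrawn; the end of data collection is inferred from 11c. The route is selective, because it needs recovery of capacity, but it is open in both arms.
- **That two hidden reoperations could reverse a clear result.** Moving from 10 versus 2 (p = 0.0098) to 10 versus 4 (p = 0.067) needs two withdrawn surgery-plus patients who are both reoperated later. Given two withdrawals unrelated to outcome, the chance is at most 0.05² = 0.25% at the planned rate, or 0.10² = 1% at 10%.

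It is also slightly too broad to say that every outcome is in the chart data: mRS is analysed in 9a but is missing from the lists of collected data in 8c and 9c. The consent pages are not available, so what subjects are told about withdrawal cannot be checked.

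**Conclusion.** The point holds as a stated rule that discards obtainable outcome data. Under 11c, reoperations and complications after withdrawal are lost, there is no option for continued record review, and the analysis plan has no rule for the patients affected.

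The supportable size is modest: power falls from 84.6% to 80.5% or 79.2% at an assumed equal 10% loss, depending on how lost patients are handled. A single unseen event can move a borderline result across 0.05. A bias favouring one arm arises only if withdrawal differs by arm or by outcome. The documents give no withdrawal rate and no evidence of such a difference, so that bias is possible but of unknown size. Confidence is high on the wording gap and low on its eventual effect. The change is worth making because it is cheap and the lost data cannot be restored at analysis.

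**What to change.** In section 11c and the consent form, distinguish two levels of withdrawal:

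1. **Stopping the procedure or active participation.** Record review for reoperation, death and AEs/SAEs continues to 3 months if the consent allows it. State explicitly that this covers patients who decline embolization.
2. **Refusing further record review.** Collection stops, and data already collected are kept.

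Put the same question to subjects who regain capacity under section 16. Record the level, date and reason for every withdrawal, and report them by arm. In section 9a, state how patients whose outcome remains unknown enter the chi-square comparison, with a sensitivity analysis.

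The cost is an IRB amendment to the protocol and consent wording. No visit or test is added. Some subjects will still refuse record review, so the loss is reduced but not removed.

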All procedures done during the course of this study are standard treatments for SDH. Patients with SDH that require surgical evacuation who agree to participate, will be randomly assigned either to a surgery group who will continue their course of care after surgery with no further intervention (unless needed as determined by standard of care) and a surgery plus group who, after surgery, will undergo endovascular embolization using standard of care embolization procedures (unless embolization is not indicated for the patient as determined by standard of care). Embolization includes cerebral angiogram with polyvinyl alcohol particle or onyx glue embolization via a catheter inserted in the groin while under general anesthesia. Patients undergoing SDH surgical evacuation are hospitalized on average 2-5 days; randomization and the embolization procedure will take place during the same hospitalization period within 72 hours after surgery. Embolization is a minimally invasive procedure and patients are typically discharged on post procedure Day 1, so the hospital stay will not be increased due to the embolization procedure. Patients will undergo a CT scan within 24 hours after surgery. This scan is standard care and will occur prior to the embolization. Approximately 4-6 weeks after the hospitalization, the patients will undergo a standard follow-up CT scan. Further scans will be done thereafter if clinically indicated. All patients will have the same follow-up care during the course of their hospitalization unless there is a complication.

These procedures, surgery and embolization, are done routinely separately and in combination for treatment of SDH. The research procedure will be the collection of data from these patients to assess whether endovascular embolization following surgical evacuation can reduce the complications of SDH.

b. Describe and explain the study design:

If the study involves multiple conditions where each condition involves different procedures, please provide a table that breaks down the procedures by condition and in chronological order. Include when and where they are performed.

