
a. Describe the data analysis plan, including any statistical procedures:
 
Data analysis will include patient age and sex, GCS score, need for redo surgery for surgical decompression of SDHs, complication rates of procedures, length of hospital stay, and follow up CT imaging findings, anticoagulant use, and history of brain trauma. All statistical analysis will be performed using SAS 9.4 and statistical significance will be assessed using an alpha level of 0.05. Descriptive statistics will be determined within surgical group (treatment or control) and will include frequencies and percentages for categorical variables, means and standard deviations for continuous variables, and medians and interquartile ranges for ordinal data.
 
To examine differences in the need for additional surgical decompression of SDH, demographic variables, CGS scores, complication rates of procedures, length of hospital stay, and follow up CT image findings a variety of statistical tests will be performed. For categorical data (additional surgical decompression of SDH, sex, complication rates of procedures, and follow up CT image findings), chi-square tests will be used to examine differences in proportions between control and treatment groups. For continuous data (age, GCS score, and length of hospital stay) two-sample t-tests will be used to examine differences in means between control and treatment groups. For the mRS score, a non-parametric Wilcoxon Rank Sum test will be used to examine differences in medians between control and treatment groups.
	 N/A																				

b. When applicable, provide a power analysis:
 
The sample size needed to examine differences in percent needing additional surgical decompression of SDH using a chi-square test at an alpha level of 0.05 was determined assuming a power of 0.80, 0.85 and 0.90. The percent needing additional surgical decompression of SDH in the control group was assumed to be 35%. The percent needing additional surgical decompression of SDH in the treatment group was assumed to be 5% and 10%. The table below shows the required sample size per group to detect differences in the percent needing additional surgical decompression of SDH between the treatment and control groups.
	N/A																				

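### Complications are compared only between the randomised groups, so surgery-plus patients who decline embolization dilute its harm; add a summary among patients in whom it was begun

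*Combined protocol and SAP*

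**What the plan says.** All references are to the combined protocol and SAP.

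- **Section 11c** lets a patient decide against embolization at any time and then states: "If the embolization procedure is not done, the patient will be included in the analysis as they were randomized". The sentence makes no distinction between effectiveness and safety outcomes.
- **Section 9a** gives the only planned comparison of complications: "For categorical data (additional surgical decompression of SDH, sex, complication rates of procedures, and follow up CT image findings), chi-square tests will be used". The comparison is between control and treatment groups. No safety population, summary by treatment received or exposed denominator is defined.
- **Section 8a** allows for surgery-plus patients who are not embolized: "unless embolization is not indicated for the patient as determined by standard of care". It does not say how they are analysed.
- **Section 11a** has patients removed when physicians decide against the procedure, and allows removal when another treatment is judged better.
- **Section 8d** makes a patient a screen failure if embolization is found to be necessary after consent.
- **Section 10g** gives the condition for suspending the research: "If the embolization procedure is associated with statistically significant increased risks to the subject". It is worded in terms of the procedure, not the assigned group, and names no test.
- **Sections 8c and 9c(i)** list the data items. Surgery is recorded, and so are complications. Whether embolization was begun is not on either list.

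**The concern.** As-randomised analysis suits redo surgery and the other effectiveness outcomes. The risk of the procedure itself is a different question. Sections 8d and 12a name groin hematoma, infection and embolic stroke as risks of embolization. A patient who never has the procedure cannot have a complication of it, yet under 11c that patient is counted in the surgery-plus denominator.

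The reported complication rate and the between-group excess are therefore both pulled toward no difference, which is the non-conservative direction for harm. A trial with few or no events would quote a denominator that includes unexposed patients. No planned analysis states the risk per patient who was embolized, although that is the figure a clinician would want and the one closest to the wording of 10g.

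**Working it through.** **The plan's own figures.** The documents give no complication rate, so there is no safety figure to reproduce. The only calculated figures are the sample sizes for redo surgery in 9b. The pooled-variance formula for two proportions (two-sided 0.05, no continuity correction) gives 27/31/36 per group for 35% v 5% and 43/49/57 for 35% v 10%, at power 0.80/0.85/0.90. All six cells match. They bear on this point only through the chosen size of 30 per group.

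**Inputs.**
- n = 30 per group (sections 4 and 9b).
- f = share of surgery-plus patients not embolized. Not given; 10% (3 of 30) and 20% (6 of 30) are assumed.
- e = average excess complication risk among embolized patients. Not given; 5, 10 and 20 percentage points are assumed.
- b = background complication risk after surgery, equal on average in the two groups by randomisation. It cancels from the difference.
- No control is embolized (section 8b).

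**Step 1: dilution of the excess.**

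As-randomised difference = [b + (1 − f)e] − b = (1 − f)e

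| Excess among embolized, e | f = 0 | f = 3/30 | f = 6/30 |
|---|---|---|---|
| 5 points | 5.0 | 4.5 | 4.0 |
| 10 points | 10.0 | 9.0 | 8.0 |
| 20 points | 20.0 | 18.0 | 16.0 |
| Share of e kept | 100% | 90% | 80% |

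Each surgery-plus patient not embolized removes 1/30, about 3.3%, of the excess.

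**Step 2: the denominator when events are seen.** Suppose three patients have a complication of embolization. As randomised the rate is 3/30 = 10.0%. Among the embolized it is 3/27 = 11.1% or 3/24 = 12.5%.

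**Step 3: the denominator when no events are seen.** The exact one-sided 95% upper limit is 1 − 0.05^(1/n).

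- n = 30: 1 − 0.905 = 9.5%
- n = 27: 1 − 0.895 = 10.5%
- n = 24: 1 − 0.883 = 11.7%

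Quoting 0/30 therefore understates the limit by 1.0 to 2.2 points.

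**Step 4: which patients the text keeps.**

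| Situation | Text | Consequence |
|---|---|---|
| Surgery-plus patient declines embolization | 11c | Kept as randomised: dilutes |
| Embolization not indicated | 8a; no analysis rule of its own | May be kept under 11c or removed under 11a: unclear |
| Physicians decide against embolization | 11a | Removed, although the 11c sentence read alone would keep the patient |
| Embolization found necessary after consent | 8d | Screen failure |
| Full withdrawal | 11c | Collection stops; data already collected are used |

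Only the first row is clearly part of f. The second may be.

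**The case against.** **The comparison is not invalid.** Comparing complications as randomised gives an unbiased answer about the effect of assignment to surgery plus embolization. That stands, and the comparison should stay. What is missing is a second summary that answers a different question.

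**The effect may be small.** Section 8a places randomization and embolization in one hospital stay, within 72 hours of surgery, so non-receipt could be low. Sample size limits the safety comparison more than dilution does. With an assumed 5% background and a 10-point excess, approximate power at 30 per group is only 0.25 with full receipt, against 0.22 or 0.19 with 3 or 6 patients not embolized. This also stands, and it favours reporting an exposed denominator with an exact interval over reliance on a test.

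A reader might infer more than the documents support in five ways:

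- *That everything is analysed strictly as randomised.* Sections 8d and 11a take some patients out of the study, so physician decisions against embolization cannot be counted as a clear source of dilution.
- *That embolized controls are charged to surgery alone.* Section 8a says the surgery group has "no further intervention (unless needed as determined by standard of care", but embolization is not named there. Section 8b says controls will not be embolized, 8d points to screen failure, and the 11c sentence covers only embolization that is not done. How a control embolized later would be analysed is not stated.
- *That the 9a test drives the suspension rule.* Section 10g names no test, and sections 10a and 10b give the DSMB all AEs and SAEs. The link is an inference.
- *That a definite loss of power can be quoted.* With an assumed 15% complication rate, no background events and f = 20%, the chance of significant harm falls from 0.68 to 0.49 by the uncorrected chi-square test, but from 0.29 to 0.14 by Fisher's exact test. Such figures depend too much on the assumed rates and the test to be relied on.
- *That the net bias is known.* Removing patients and stopping data collection at withdrawal may also hide complications, to an extent the documents do not allow one to judge.

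**Conclusion.** The point holds as a cheap improvement. Followed as written, 11c and 9a keep surgery-plus patients who decline embolization, and possibly those in whom it is not indicated, in the denominator for its complications, and no analysis by exposure is planned. The excess is diluted to (1 − f) of its value among embolized patients: 90% to 80% for f = 10% to 20%, with a zero-event upper limit of 9.5% in place of 10.5% to 11.7%.

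The proportional form follows from the plan, given that no control is embolized. The values of f are illustrative, because the documents give no rates. The result does not undermine the as-randomised comparison or the sample size. Separately, sections 8a, 8d, 11a and 11c do not agree on whether patients who depart from their assignment are kept, removed or called screen failures, so the denominator for safety is not fully defined.

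**What to change.** 1. Keep the as-randomised comparison for the effectiveness outcomes and for the between-group complication comparison.
2. Add to 9a: *Complications of embolization are also reported among all patients in whom embolization was begun, with that number as denominator and an exact 95% confidence interval, and complications are also tabulated by treatment received.*
3. Add to the data lists in 8c and 9c(i) a field for whether embolization was begun.
4. Give the DSMB both tables, since 10g is worded in terms of the procedure.
5. Reconcile sections 8a, 8d, 11a and 11c on who is kept in the analysis, removed or called a screen failure. The choice of clinical rule is for the investigators; the analysis text needs one consistent statement of what follows from it.

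Cost: one sentence, one data field and one extra table, plus the reconciliation. Downside: the by-treatment-received table is not protected by randomisation, because patients who decline may differ from those who accept. It should sit beside the as-randomised table and not replace it.
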